Official Title in ClinicalTrials.gov: Treatment for Nicotine Addiction in Women

NCT: NCT02448654

Document Date: 7/7/14

<from originally planned analysis section- from grant>

Sample Size Considerations and Data Analysis

Power Analysis: As this is the first randomized clinical trial evaluating the effect of tolcapone on withdrawal, smoking urges, and cognition in women smokers during abstinence, we used effect sizes from comparisons of Val158Met genotype as general proxies for treatment differences. In previous research, we found significant differences in women smokers by Val/Val vs. Met/_ genotype in withdrawal (F= 5.7, df=48, p=.02), smoking urges (F= 16.9, df=48, p<.001), and sustained attention (F=9.9, df=48, p=.003) during abstinence, and subjective ratings of nicotine's anxiolytic effects (F=3.7, df=47, p=.02) (see Preliminary Data). Using G*Power, we found that with a sample of 60, alpha=.05, power=.80, we would be able to detect large effects for our planned analyses (f=.37). We expect to enroll 80 subjects to achieve a completion N=60. However, with N=52 we would still be able to detect a large effect size (f=.40).

Analysis Plan: The primary statistical models will be analysis of covariance (ANCOVA) to test for medication group differences in withdrawal, smoking urges, sustained attention and smoking choice post-abstinence. COMT genotype will be used as an independent variable in an exploratory two factor ANCOVA. Menstrual cycle phase, race and baseline smoking severity will be included as covariates.

Specific Aim 1: ANCOVAs will examine the effect of tolcapone on reducing a) withdrawal severity (MNWS); b) smoking urges (BQSU); and c) cognitive impairment (e.g., CPT) during abstinence vs. placebo. With 80% power, we can detect a large medication effect (f=.37). Specific Aim 2: ANCOVA will examine the effect of medication vs. placebo on laboratory smoking choices post-abstinence. With 81% power, we can detect a large effect (f=.40). Exploratory Aim 1: ANCOVAs will examine the effect of Met/_ genotype on reduced a) withdrawal severity (MNWS); b) smoking urges (BQSU); and c) cognitive impairment (e.g., CPT) during abstinence vs. Val/Val. With 80% power, we can detect a large genotype effect (f=.37). Exploratory Aim 2: ANCOVA will assess withdrawal and smoking post abstinence, using both medication and genotype as the independent variables and co-varying for baseline scores, to test for a medication by genotype interaction. With 81% power, we can detect a large effect (f=.40).

Exploratory Aim 3: Structural equation modeling will examine moderating effects of gonadal hormone levels on withdrawal severity and smoking behavior post-abstinence. The mediation effect size is unknown.

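### Do the mismatched F and p value and the unlabelled power figures in the SAP's sample size section undermine the planned N?

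*SAP*

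**What the plan says.** The Power Analysis paragraph of the SAP explains that, with no earlier trial of tolcapone in this setting, "we used effect sizes from comparisons of Val158Met genotype as general proxies for treatment differences". It then lists four Val/Val against Met/_ comparisons in women smokers and calls them all significant. Three concern Aim 1 outcomes: "withdrawal (F= 5.7, df=48, p=.02"), smoking urges (F=16.9 on 48 df, p<.001) and sustained attention (F=9.9 on 48 df, p=.003). The fourth is "subjective ratings of nicotine's anxiolytic effects (F=3.7, df=47, p=.02"). The numerator df is not printed for any of them.

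The sample size statement follows: "with a sample of 60, alpha=.05, power=.80, we would be able to detect large effects for our planned analyses (f=.37"). The SAP plans to enrol 80 so that 60 complete, and adds: "However, with N=52 we would still be able to detect a large effect size (f=.40").

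The aim-by-aim text gives 80% power at f=.37 for Specific Aim 1. For Specific Aim 2 it says: "ANCOVA will examine the effect of medication vs. placebo on laboratory smoking choices post-abstinence. With 81% power, we can detect a large effect (f=.40"). The same figure recurs under Exploratory Aim 2: "to test for a medication by genotype interaction. With 81% power, we can detect a large effect (f=.40"). No N stands beside any of these. On covariates, the Analysis Plan says: "Menstrual cycle phase, race and baseline smoking severity will be included as covariates".

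Section 5.A (Overview) of the Protocol gives the size of the study as 60 women smokers and does not say whether they are enrolled, randomized or completing.

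**The concern.** Four things catch the eye.

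1. One of the four F and p pairs cannot be right for a two-group comparison, yet it is listed as significant. An arithmetic fault in the sample size paragraph raises doubt about the rest of it.
2. The genotype effects are offered as stand-ins for the drug effect, but the SAP never converts them to f. Converted directly, withdrawal falls below the detectable .37. Withdrawal is the first outcome under Aim 1, so a reader of a null result might think the trial had 80% power at the proxy when it had less. Smoking choice, the Aim 2 outcome, has no proxy at all.
3. Aim 1 and Aim 2 appear to be powered at different sample sizes, and neither is labelled.
4. If the Protocol's 60 were the number enrolled, the loss implied by the SAP (1 − 60/80 = 25%) would leave 45 completers. Power at f=.37 would then be 68.0%.

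**Working it through.** **Inputs.** From the SAP: alpha .05, power .80, N=60 and 52, f=.37 and .40, the four F values with their denominator df, 80 enrolled and 60 completing. Assumed: two arms of equal size (the ratio is not stated) and a non-directional F test.

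**The SAP's own figures.** Power comes from the noncentral F with 1 and N−2 df and noncentrality λ = f²N.

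| f | N | λ | Critical F | Power |
|---|---|---|---|---|
| .37 | 60 | .1369 × 60 = 8.21 | 4.007 | 80.5% |
| .40 | 52 | .16 × 52 = 8.32 | 4.034 | 80.7% |
| .40 | 60 | .16 × 60 = 9.60 | 4.007 | 86.1% |

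Solving for f at exactly 80% power gives .368 at N=60 and .396 at N=52. With up to six covariate df removed, these become .369 and .397. Both stated detectable effects are right.

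**The F and p pairs.** Upper tail of F with 1 numerator df, as for two groups:

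| Measure | F (denominator df) | Printed p | Recomputed p |
|---|---|---|---|
| Withdrawal | 5.7 (48) | .02 | .021 |
| Urges | 16.9 (48) | <.001 | .00015 |
| Attention | 9.9 (48) | .003 | .0028 |
| Anxiolytic rating | 3.7 (47) | .02 | .060 |

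Three fit and one does not. Rounding of F does not explain it (3.65 to 3.75 gives .062 to .059), and neither does halving p for a one-sided test (.030). On 1 and 47 df, p=.02 needs F of about 5.8. With 2, 3 or 4 numerator df, F=3.7 gives .032, .018 or .011, so a 3-df test would round to the printed value.

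**The proxies as effect sizes.** With 1 numerator df, f = √(F/df₂):

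- withdrawal: √(5.7/48) = .345
- urges: √(16.9/48) = .593
- attention: √(9.9/48) = .454

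At .345, power is 74.7% with 60 completers and 68.3% with 52, if the covariates explain nothing. This direct conversion ignores how the genotype groups were split. To carry a mean difference into equal arms, take d = √[F(1/n₁ + 1/n₂)] and f = d/2. With F=5.7 and an assumed total of 50 (48 + 2):

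| Split | d | f in equal arms | Power at N=60 |
|---|---|---|---|
| 50/50 | .675 | .338 | 73.0% |
| 40/60 | .689 | .345 | 74.7% |
| 30/70 | .737 | .368 | 80.1% |
| 25/75 | .780 | .390 | 84.4% |

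The documents do not give the split. Covariates also matter: with f/√(1−R²), an assumed R² of 12% raises power at f=.345 and N=60 to 79.9%. The 95% interval for the withdrawal f, found by inverting the noncentral F, runs from about .04 to .62.

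**The 81% at f=.40.** It agrees with N=52 (80.7%) and not with N=60 (86.1%). The interaction test in Exploratory Aim 2 (1 numerator df, four cells) gives the same two figures.

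**60 and 80.** 60/(1 − .25) = 80, which agrees with the SAP's enrolled and completing numbers.

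**The case for a change.** The best case for a change is that each item can be checked and would cost a few words to settle. A p-value that does not follow from its F stands in a sentence claiming significance. Power for two aims rests on two sample sizes without saying so. The SAP invites the reader to treat genotype effects as a guide to the drug effect but leaves out the comparison that would show withdrawal close to, or below, what the trial can detect.

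The first part stands as a fact: as a two-group comparison the pair is inconsistent. But the numerator df is not printed, and the Protocol's Background describes the anxiety result under both placebo and nicotine administration, so a test with several df cannot be ruled out. The second part also stands, as missing detail only. The SAP ties f=.40 to N=52 in the Power Analysis paragraph, so the N can be recovered, and the figure errs on the cautious side for 60 completers.

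The third part is weaker. The SAP calls the comparisons general proxies and does not claim that each reaches .37. Whether withdrawal falls short turns on an unreported genotype split, and the interval for that effect easily includes .37. Writing 75% and 68% into the plan would present as settled two figures that the documents cannot establish. The absence of a proxy for smoking choice leaves the detectable effect for Aim 2 as it was. The 45-completer reading has no support, because the SAP labels 80 as enrolled and 60 as completing.

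**Conclusion.** No change follows. The figures that carry the sample size, f=.37 at N=60 and f=.40 at N=52, are correct to rounding under equal allocation and a non-directional test, so the plan has the power it states.

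The anxiolytic entry (p=.060 against the printed .02, on 1 numerator df) is best read as a clerical slip or an unprinted numerator df. It is a background statistic, it is not one of the outcomes in the ANCOVAs, and correcting it would move no N, power figure or analysis. The 81% at f=.40 is the N=52 figure and understates power at 60 completers by about 5 percentage points (86.1% − 80.7%). The Protocol's 60 is naturally read as completers, since the SAP spells that out.

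The withdrawal proxy gives between 73% and 84% power at N=60 for splits from 50/50 to 25/75, before any gain from covariates. That range lies on both sides of 80% and does not contradict anything the SAP claims. An analyst would run the same ANCOVAs on the same women either way.

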## 5. Research Plan:

### A. Overview

The proposed study will assess the effects of the COMT inhibitor, tolcapone, versus placebo on reducing withdrawal symptoms (including cognitive decrements), smoking urges and smoking behavior, in women smokers. This will be a double-blind, placebo-controlled study, with 60 women smokers. After completing an *ad libitum* smoking baseline, participants will be randomized to 8-days of the COMT inhibitor tolcapone (100mg three times a day (TID) for 7 days then 100mg once on day 8) or placebo (Apud *et al*, 2007; Grant *et al*, 2013). For the first two days of the medication period, participants will continue to smoke *ad libitum* and attend brief check-in sessions once daily to take one dose and be given the remaining two doses to take at home. On medication days 3-5, they will be given take-home doses and will be asked to check in daily by phone or in person and continue to smoke *ad libitum*. On the evening of medication day 5, the 60-hr (2 ½ day) abstinence period will begin. During the 2 ½ day abstinence period, participants will attend brief check-ins daily, to receive their dose (plus take-home doses) and to be screened for abstinence adherence (breath CO levels; urine cotinine). Measures of withdrawal and smoking urges will be collected at all sessions. On Medication Day 8, a test session will be conducted where assessment of cognitive function and smoking behavior will be collected. At the conclusion of the session on Medication Day 8, subjects will be stop the medication. A brief follow-up session will be completed approximately 1-week after the final medication day then subjects will be discharged from the study. A between-subject design will be used since the study involves numerous visits and several days of abstinence and we predict that a within-subject design would be overly burdensome to participants and result in high attrition rates. A between-subject design also avoids possible medication carryover effects.

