Minnesota Nicotine Withdrawal Symptom Checklist (MNWS): At all sessions except screening, smokers will be asked to rate nicotine withdrawal symptoms (cigarette craving, irritability/anger, anxiety/tension, difficulty concentrating, restlessness, increased appetite, depressed mood, and insomnia) on a 100 mm scale, "not at all" to "extremely" (Hughes and Hatsukami, 1986).

Brief Questionnaire on Smoking Urges (BQSU): This 10-item scale reliably measures cigarette craving (Tiffany and Drobes, 1991) and will be administered at all sessions except screening.

Positive and Negative Affect Schedule (PANAS): The PANAS is a 20-item scale that assesses both negative and positive affective states (Watson *et al*, 1988). This scale is sensitive to the affective symptoms of tobacco withdrawal and predicts relapse to smoking (Kenford *et al*, 2002) and will be administered at all sessions except screening.

Premenstrual Assessment Form (PAF): Given their potential overlap with withdrawal symptoms (Allen *et al*, 1996; Allen *et al*, 1999; Carpenter *et al*, 2006), premenstrual symptoms will be assessed with the 10-item PAF (Halbreich *et al*, 1982) at all sessions except screening so they can be used as covariate in analyses focusing on withdrawal symptoms.

Drug Effects Questionnaire (DEQ): Smokers will rate 10 items that are related to nicotine effect on a 100 mm scale, "not at all" to "extremely." The items are feeling "stimulated", "high", "anxious", "sedated", "down", "good drug effects", "bad effects", "drug strength" as well as

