#### Individual Stopping Rules:

For the purposes of participant safety and data quality control, subjects will be discharged from the medication trial if: 1) subject experiences serious side effects which appear related to the study medication including liver toxicity (LFT>2 times greater than the upper limit of the normal range); 2) study physician/medical monitor decides that continued study participation may cause physical or psychological harm to the subject; 3) subject misses 3 consecutive medication-administration study sessions; 4) subject misses 2 consecutive CO level tests, urine cotinine tests during the abstinence phase; 5) subject is found to have used alcohol, illegal drugs or other psychotropic drugs during the medication phase of the study. In the case of any of these causes of early discharge from the trial, participants who began the medication phase of the study- even if they did not complete the medication phase- will still be contacted for phone follow-up and invited to attend the in person follow-up check-in for safety purposes.

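### The post-abstinence ANCOVA has no stated analysis set or missing-data rule, and no specified model uses the Day 6 and 7 withdrawal and urge scores

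*SAP*

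**What the plan says.** **Size.** The SAP (Power Analysis) states: "We expect to enroll 80 subjects to achieve a completion N=60". The calculation is for "with a sample of 60, alpha=.05, power=.80", giving a detectable f of .37, with a fallback of f=.40 at N=52. The protocol (5.A Overview) says: "This will be a double-blind, placebo-controlled study, with 60 women smokers". It mentions neither 80 nor completers.

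**Model.** The SAP (Analysis Plan) names ANCOVA for withdrawal, urges, sustained attention and smoking choice after abstinence. The covariates are menstrual cycle phase, race and baseline smoking severity. Adjustment for the baseline score of the outcome is mentioned only for Exploratory Aim 2. Specific Aim 1, in contrast, speaks of withdrawal, urges and cognition during abstinence.

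**Discharge.** The protocol (Individual Stopping Rules) discharges women for serious drug-related side effects, physician judgement, three consecutive missed medication sessions, two consecutive missed abstinence-phase CO or cotinine tests, and alcohol or drug use. Those who had begun medication "will still be contacted for phone follow-up and invited to attend the in person follow-up check-in for safety purposes". No Day 8 test session is described for them.

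**Measurements.** The protocol (Subjective/Questionnaires) gives "Minnesota Nicotine Withdrawal Symptom Checklist (MNWS): At all sessions except screening", and the same timing for the BQSU. Study Procedures places in-person visits on abstinence Days 6 and 7. Cognitive tasks are done at baseline and Day 8 only, and the Smoking Choice Paradigm once, on Day 8.

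**The concern.** An ANCOVA of Day 8 scores can use only women who have Day 8 scores. Without a rule for the others, software drops them, and the comparison is between those who stayed rather than between the groups as randomised. Side effects can differ by arm. Missed abstinence tests can follow from severe withdrawal, which is itself the outcome. If loss runs along either path, the contrast can be biased, and the direction depends on who leaves from which arm.

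For withdrawal and urges, part of the remedy is already in the data: two further abstinence-day scores per woman. Aim 1 as worded covers those days, but the SAP does not say which day, or what combination of days, is tested.

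**Working it through.** **1. The plan's own figures.** Inputs from the SAP: alpha .05, power .80, f=.37 at N=60, f=.40 at N=52. Equal allocation is assumed, since no ratio is stated. Noncentral F with 1 numerator df and λ = N × f²:

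- N=60: λ = 60 × .37² = 8.21. Power is .805 without covariates and .804 with three. Detectable f at 80% power is .368, so d = 2f is about 0.74.
- N=52: λ = 52 × .40² = 8.32. Power is .808 without covariates and .807 with three.
- Enrolment: 60 / (1 − 0.25) = 80, a 25% loss. N=52 out of 80 is a 35% loss.

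All stated figures reproduce.

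**2. How many are lost after randomisation?** The documents do not say. Consent is taken at screening, before eligibility is settled, and randomisation follows the *ad libitum* baseline. If all 80 are randomised, 20 are lost afterwards (25%). If 80 are consented and 60 randomised, the 20 losses fall before randomisation and cause no imbalance between arms.

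**3. Size of a bias, by formula (illustrative).** Let p be the proportion lost and δ how much worse leavers would score than stayers in the same arm, in SD. The completer contrast (tolcapone minus placebo, higher = worse) is shifted by p_C × δ_C − p_T × δ_T.

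- Assumed loss of 35% on tolcapone and 15% on placebo, δ = 0.5 to 1 in both arms: (0.15 − 0.35) × 0.5 to 1 = −0.10 to −0.20 SD, which flatters tolcapone. That is 14% to 27% of 0.74.
- Same losses, but tolcapone leavers no worse than stayers (δ_T = 0): 0.15 × 0.5 to 1 = +0.075 to +0.15 SD, against tolcapone.

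**4. Size of a bias, by simulation (illustrative).** Assumptions: SD 1, correlation 0.6 between all visits, 25% lost overall, a chance of leaving that rises with withdrawal (log-odds slope 0.75 or 1.5 per SD), and 400,000 women per arm. The last column fills missing Day 8 scores by regression within arm on baseline and Day 6, standing in for a likelihood-based mixed model.

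| Loss driven by | True effect (SD) | Completer ANCOVA | Using Day 6 scores |
|---|---|---|---|
| Day 6 score (seen) | 0.74 | 0.703 to 0.724 | 0.739 to 0.743 |
| Day 6 score (seen) | 0.50 | 0.474 to 0.495 | 0.501 to 0.505 |
| Day 8 score (unseen) | 0.74 | 0.636 to 0.698 | 0.643 to 0.703 |
| Day 8 score (unseen) | 0.50 | 0.429 to 0.472 | 0.434 to 0.474 |

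With no true effect and the same loss process in both arms, the bias is zero. Repeated scores remove the bias when loss depends on what was seen, and do almost nothing when it depends on the unseen Day 8 value.

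**5. Who could be helped.** A woman discharged for missing tests on Days 6 and 7 has no abstinence score. One who misses Days 7 and 8 has Day 6 only. A woman who leaves during Days 1 to 5 has none.

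**The case against.** The strongest case against is that the SAP, a short extract from the grant, omits a rule rather than choosing a bad one. Several stronger readings are tempting and are not supported.

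- A reader might infer that the SAP declares a completer analysis. It does not. The sentence on 80 and 60 is about recruitment and sizing; the completer analysis is only the default when nothing else is specified.
- A reader might infer that the SAP expects outcome-related discharges, or that 25% are lost after randomisation. Neither is stated. A smoking lapse costs a bonus payment and is not a listed discharge reason. Liver tests after screening are scheduled on Day 8 and at follow-up, so the one side effect named in the stopping rules would not, on schedule, remove a woman before the Day 8 session.
- A reader might infer that Days 6 and 7 recover most of a missing Day 8 score. At an assumed within-woman correlation of .7, the share is 2r²/(1+r) = 0.98/1.7 = 58%, but only for a woman with both scores. With Day 6 alone it is r² = 49%, and with neither it is nil. The discharge rules on missed visits often leave one score or none.
- A reader might infer that the fix lowers detectable f from .368 to .317. That needs 80 women randomised with full information. A mixed model retains nobody, so this gain should not be claimed.

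It is also fair that an ANCOVA with a stated missing-data rule would close much of the gap. What remains is that no set and no rule is given, and that relevant scores already collected have no stated use.

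**Conclusion.** The point holds as an omission with a cheap remedy. By default, the planned test of withdrawal and urges leaves out randomised women without Day 8 scores, for reasons that could relate to arm or outcome, while the abstinence scores from Days 6 and 7 enter no specified model.

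The size cannot be fixed from the documents. Under the assumptions shown, shifts range from none, through 0.02 to 0.10 SD in the simulation at a true effect of 0.74 (0.74 − 0.724 and 0.74 − 0.636), to 0.20 SD under the 35% versus 15% split, in either direction. The loss split, the severity of leavers and the correlations are all assumed.

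The benefit of repeated scores is confined to MNWS and BQSU. Smoking choice and CPT have no Day 6 or 7 values and gain little. The power figures need no change. The change should be made, but the documents do not show that the trial's result would be materially wrong without it.

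**What to change.** In the SAP:

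1. Define the primary analysis set as all randomised women, by assigned arm. State what enrolment means, and reconcile the SAP's 80 and 60 with the protocol's 60.
2. For MNWS and BQSU, replace the single ANCOVA with a mixed model on Days 6, 7 and 8: arm, day, arm-by-day, baseline score of the outcome and the listed covariates. Name the Day 8 contrast as the test. This also settles the time point for Aim 1.
3. For CPT and smoking choice, keep the ANCOVA on available Day 8 data by assigned arm, adding the baseline score for CPT. Smoking choice has no baseline value. Add multiple imputation as a sensitivity analysis.
4. Report losses after randomisation, with reasons, by arm.

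**Cost:** SAP wording and modest extra analysis, with no new visits or measurements. The mixed model assumes data missing at random. It helps only women with at least one abstinence-day score, and it does not correct loss driven by unseen Day 8 values.

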### *Biochemical*

Genetics: Blood samples for DNA extraction will be collected at screening to examine whether the Val158Met single nucleotide polymorphism (SNP) of the COMT gene modifies the effects of nicotine. To protect confidentiality, each subject's blood sample will be encoded with a numeric designation and the name of the individual will be stored in a separate database. The samples will be transferred to the Genetic Laboratory at the VA medical Center for processing and storage.

Laboratory Bloods: Standard laboratory blood screening will include liver and thyroid function tests, CBC, serum electrolytes, BUN, creatinine, PT and PTT. This will be done at screening, again at the post-2 ½ day abstinence testing session and at the 1-week follow-up.

Urine screens: Urine pregnancy screens will be administered at screening, *ad libitum* baseline, prior to medication initiation, and prior to Smoking Choice Paradigm at the post-abstinence final session and at the 1-week follow-up. Urine drug screens will be administered at screening, *ad libitum* baseline, prior to medication initiation, and at the post-abstinence final session. Urine cotinine levels will be measured at baseline and check-in sessions and at post-abstinence testing session.

Serum estradiol and progesterone analysis: Serum estradiol and progesterone levels will be measured before the *ad libitum* smoking baseline and post-abstinence final session for use as covariates in our analysis, since female sex hormones may contribute to variation in women's response to nicotine or withdrawal (Allen *et al*, 2009b; DeVito *et al*, 2013) or women's smoking cessation ability (Allen *et al*, 2008a).

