## COMT Inhibition as a Novel Treatment for Nicotine Addiction in Women

(tolcapone) or placebo, in a double-blind fashion. Urn randomization will endeavor to balance medication and placebo groups for race, baseline smoking rate, and menstrual cycle phase. Although genotype will not be known for all subjects prior to randomization, in cases when it is known (e.g., genetics sample collected at baseline is processed prior to randomization) will be counterbalanced for genotype as much as possible.

Brief once-daily visits during the medication initiation (Medication Days 1-2) and abstinence periods (Medication Days 6-7) will serve four purposes: 1) administer pill in person and give take-home doses with instructions (100mg three times a day (TID); subjects will be asked to self-administer the take-home doses at approximately 6-hour intervals); 2) screen for adverse medication effects (Adverse Events Form; heart rate and blood pressure); 3) check for nicotine abstinence compliance (expired CO; urine cotinine; self-reported cigarettes per day); 4) collect self-report measures of withdrawal, smoking urges and mood, which are hypothesized to fluctuate with abstinence and/or medication.

Medication Initiation and Stabilization Phase (Medication Days 1-5): For the first five days of medication, subjects will be told they may smoke their cigarettes as much as they choose (*ad libitum*). They will be asked to attend one brief session per day on Medication Days 1-2. These first days will allow the participants to achieve medication optimal dosing and steady state levels prior to initiating the abstinence period. For Medication Days 3-5, the subjects will maintain the same dose and take the doses at home. During these days, they will have either in person/or phone check-in with a member of the research team to check for reported adverse effects. Brief questions about smoking (e.g., cigarettes per day) and whether they noticed changes in mood or smoking urges will also be asked. These phone check-in days are designed to maintain contact to continue monitoring for safety purposes, while reducing the burden on the participants. Subjects will have an emergency contact so they can access care if needed during this time.

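### The primary ANCOVAs leave out COMT genotype, a baseline variable the trial already collects; adding it would buy a modest, nearly free gain in precision

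*SAP*

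**What the plan says.** The SAP's Analysis Plan names ANCOVA as the primary model for four post-abstinence outcomes: withdrawal, urges, sustained attention and smoking choice. The covariates are cycle phase, race and smoking severity at baseline. Genotype has a separate role: "COMT genotype will be used as an independent variable in an exploratory two factor ANCOVA". Exploratory Aim 1 looks at genotype main effects. Exploratory Aim 2 fits medication and genotype together, but names only withdrawal and smoking.

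The Power Analysis paragraph of the same document reports earlier genotype comparisons in women smokers: "genotype in withdrawal (F= 5.7, df=48, p=.02", and "smoking urges (F= 16.9, df=48, p<.001), and sustained attention (F=9.9, df=48, p=.003) during abstinence". It uses them as stand-ins for the size of the treatment effect. It then states that "with a sample of 60, alpha=.05, power=.80, we would be able to detect large effects for our planned analyses (f=.37".

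In the protocol, section 5.B (Biochemical, Genetics) says "Blood samples for DNA extraction will be collected at screening". Section 5.E names race, smoking rate and cycle phase as urn factors, and adds that where genotype is known before randomisation, allocation "will be counterbalanced for genotype as much as possible".

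**The concern.** Genotype has the properties wanted in a baseline covariate. Treatment cannot change it, collection is already planned, and it is the only predictor of these outcomes for which the SAP gives numbers. It also plays a part in allocation, whereas the three urn factors all reappear as primary covariates and genotype does not. Leaving it out keeps whatever variance it explains in the error term of the medication comparison. In a trial with about 30 completers per arm and 80% power only for a large effect, a small loss of precision is worth recovering if it costs almost nothing. The adjustment has to be prespecified, because adopting it after seeing results would be post hoc.

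**Working it through.** **Inputs.** From the SAP: F=5.7, 9.9 and 16.9 on 48 error df; N=60, alpha .05, f=.37; fallback N=52, f=.40. Assumed: one numerator df for Val/Val vs Met/_, equal arms, a two-sided test, one df for each planned covariate, and f measured on the scale left after those covariates. The one-df reading fits the reported p values: the three F values give p=.021, .0028 and .00015, against the SAP's .02, .003 and <.001.

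**Step 1: reproduce the plan.** Power comes from the noncentral F with numerator df 1 and noncentrality N × f². At N=60, f=.37 it is 80.5% with no covariates and 80.4% with three. At N=52, f=.40 it is 80.7%. Both agree with the SAP.

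**Step 2: variance explained.** Partial R² = F/(F+48).

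**Step 3: equal genotype effect in both arms.** Adjusted f = .37/√(1−R²), with denominator df 54.

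**Step 4: tolcapone removes the gap, so it exists on placebo only.** The average genotype effect is halved and its squared effect size is quartered, from F/48 to F/192. So R² = (F/192)/(1+F/192).

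| Outcome | R², step 2 | Adjusted f | Power, equal effect | R², step 4 | Power, placebo only |
|---|---|---|---|---|---|
| Withdrawal | 5.7/53.7 = .106 | .391 | 84.5% | .029 | 81.5% |
| Attention | 9.9/57.9 = .171 | .406 | 87.1% | .049 | 82.3% |
| Urges | 16.9/64.9 = .260 | .430 | 90.5% | .081 | 83.5% |

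The starting point in every row is 80.4%. Counting the variance of the interaction in step 4 lowers R² slightly, to .028, .047 and .075. Power for urges is then 83.3%, and the other two change by 0.1 point or less.

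**Step 5: downside.** If genotype explained nothing, power would go from 80.39% to 80.37%.

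**Step 6: uncertainty.** Inverting the noncentral F gives 95% limits for the explained share of roughly 0-28% (withdrawal), 2-35% (attention) and 7-44% (urges).

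**Step 7: chance imbalance.** Let p be the share of Val/Val women. The genotype gap in residual SDs is √[(F/48)/(p(1−p))], and the standard error of the imbalance with 30 per arm is √[2p(1−p)/30]. The product is √[2(F/48)/30], so p cancels. For urges it is √(2 × .352/30) = 0.15 SD for a one-standard-error imbalance with no counterbalancing, or about 0.08 SD if the gap exists on placebo only.

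**Step 8: missing genotypes.** Under the placebo-only case, complete-case analysis with 58 (withdrawal), 57 (attention) or 55 (urges) women returns power to about 80%. Losing 2, 3 or 5 of 60 women would therefore erase the gain.

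**The case against.** The strongest reply is that the larger gains depend on the scenario that suits this trial least. Section 3 of the protocol says tolcapone inhibits COMT about as much as the Met allele does, and the SAP uses genotype differences as a proxy for the drug effect. If that reasoning is right, tolcapone should narrow the genotype gap and an additive term would recover only 1 to 3 points of power. This stands, and it is why the lower range comes first in the conclusion.

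The evidence is also indirect. It comes from about 50 women, section 3 describes overnight abstinence rather than some 60 hours on study drug, and the results were cited because they were significant. The models behind the F values are not shown, so the increment beyond race, already a covariate, is unknown. Nothing is reported for smoking choice. All of this stands and limits the size of the benefit.

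The SAP's choice is also coherent: its covariates match the stated urn factors, and genotype is balanced only opportunistically. Exploratory Aim 2 will give a genotype-adjusted medication estimate for withdrawal and smoking. That is a fair defence of validity. It does not help the primary tests, and Aim 2 does not name urges or attention.

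A reader might infer that omitting genotype biases the comparison, because women genotyped late are not balanced on it. The documents do not support that. Randomisation makes such imbalance random error, which the unadjusted standard error already reflects; the shift in step 7 restates the precision point.

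**Conclusion.** The point holds as a precision improvement. At N=60 and f=.37, adding genotype would raise power from 80% to about 82-84% for withdrawal, attention and urges if tolcapone removes the genotype gap, and to at most about 85-91% if genotype acts equally in both arms. Both ranges take the preliminary F values at face value and assume no overlap with the existing covariates. A reader might take 11-26% as the variance this trial is losing; that is an upper scenario drawn from a small, different setting. Nor do the documents support reading the trial as underpowered: the planned analysis is valid and its stated power reproduces. The case for change rests on the asymmetry: some likely gain against a loss of under 0.1 point if genotype turns out not to matter, provided no women are dropped.

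**What to change.** In the SAP's Analysis Plan, prespecify COMT genotype (Val/Val vs Met/_) as an additive covariate in the primary ANCOVAs for withdrawal, urges and sustained attention. Smoking choice may be included for consistency, without claiming a gain. Apply this to every randomised woman in the analysis, whether or not her genotype was known at allocation. Code a missing or failed genotype as its own category so that nobody is excluded. Keep the medication-by-genotype interaction exploratory.

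The cost is a sentence or two of SAP text, one degree of freedom for genotype and one more if any genotype is missing. No new data are needed. The wording should be fixed before unblinding.
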